5.6. Self-assessment Questionnaire (N=60)

- > Self-Assessment Questionnaire on product efficacy will be answered by subjects at T14d (after pretreatment), T25d (10-day after self-recovery), T32d (7-day after product treatment), T39d (14-day after product treatment) for Group 1 (N=30);
- ➤ **Self-Assessment Questionnaire on cosmeticity** will be answered by subjects at T14d (after pretreatment), T39d (after product treatment) for Group 1 (N=30).
- > Self-assessment questionnaire on post-procedure tolerance will be answered by subjects at T15d (Timm post-procedure), T16d (1-day after self-recovery), T18d (3-day after self-recovery), T22d (7-day after self-recovery), T25d (10-day after self-recovery) for all groups (N=60).

6. Product

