Evaluation visit on T14d

- a. Subjects wash face with usual cleanser, then pat dry with clean tissue paper at center.
- b. Acclimatization to the room condition for 30 minutes (the conditions with a well-controlled room temperature (21 ± 1 °C) and humidity ($45\%\pm5\%$).
- c. Clinical Assessment will be done by dermatologist for T14d.
- d. VISIA 7 will be done by trained technician for T14d.
- e. OCT scan will be done by trained technician for T14d.
- f. Corneometer will be done by trained technician for T14d.
- g. Vapometer will be done by trained technician for T14d.
- h. Cutometer will be done by trained technician for T14d.
- i. pH meter will be done by trained technician for T14d.
- j. LA sting test will be done by trained technician for T14d.
- k. Self-assessment questionnaire will be answered by subjects for T14d.
- l. The investigational products and standard products will be weighted and returned to subjects, meanwhile, the daily log will be also checked.
- m. Adverse Events/Local Intolerance will be checked and recorded

Chemical Procedure visit and Timme evaluation on T15d

- a. Subjects wash face with usual cleanser, then pat dry with clean tissue paper at center.
- b. One questionnaire should be answered by subjects.
- c. Pre-process of xxx for procedure preparation.
- d. CO2-laser will be done by medical technologist.
- e. Clinical Assessment will be done by dermatologist for Timm post-procedure.
- f. VISIA 7 will be done by trained technician for Timm post-procedure
- g. OCT scan will be done by trained technician for Timm post-procedure
- h. Corneometer will be done by trained technician for Timm post-procedure
- i. Vapometer will be done by trained technician for Timm post-procedure
- j. Cutometer will be done by trained technician for Timm post-procedure
- k. pH meter will be done by trained technician for Timm post-procedure
- 1. Adverse Events/Local Intolerance will be checked and recorded.

Evaluation visit on T16d (1-day after self-recovery)

- a. Clinical Assessment will be done by dermatologist for T16d.
- b. VISIA 7 will be done by trained technician for T16d.
- c. OCT scan will be done by trained technician for T16d.

- d. Corneometer will be done by trained technician for T16d.
- e. Vapometer will be done by trained technician for T16d.
- f. Cutometer will be done by trained technician for T16d.
- g. pH meter will be done by trained technician for T16d.
- h. Self-assessment questionnaire will be answered by subjects for T16d.

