8.3. Efficacy Verification

8.3.1 Comparison between Time-points

A Shapiro-Wilk test will be used to test for normality of the baseline data (T0) and the change from baseline data (Tn-T0) at post-baseline time points at significance level alpha=0.01. When data passes normality (all normality of the distributions is confirmed for the same parameter), a parametric test will be used to test the null hypothesis that the mean change from baseline is zero. When data fails normality (if one or more normality of the distributions for the same parameter is rejected), a non-parametric test will be used.

Pre-treatment efficacy:

- a) T14d (after pre-treatment), T15d (Timm post-procedure) versus T0 (baseline)
- b) T16d (1-day after self-recovery), T18d (3-day after self-recovery), T22d (7-day after self-recovery), T25d (10-day after self-recovery) versus T15d (Timm post-procedure)

Post-treatment efficacy:

a) T32d (7-day after product treatment), T39d (14-day after product treatment) versus T25d (product treatment start)

The following will be calculated and reported for each evaluation parameter at applicable post-statistical baseline time point(s):

For self-assessment questionnaires, only the data of completing subjects will be analyzed. Questionnaire response options will be in the form of a 5-point semi-structured scale, ranging from one (1) to (5), where the score of one (1) will be the most negative/unfavorable rating and the score of five (5) will be the most positive/favorable rating the product can receive (the scale will also include a mid-point label "neither agree nor disagree"). Responses obtained for each question will be tested for normality using a Shapiro-Wilk test at significance level alpha=0.01, and if the data passes normality testing, mean scores will be used. Responses that are not normally distributed will be assessed using the median response. The percentage of ratings from

4 to 5 ("top XX box %") will be reported.

In the report appendices, raw data and open-ended questionnaire responses will be listed by subject. Data frequency and percentage will be presented for questionnaires and tolerability evaluations. Tolerability tables will also be sent to the Sponsor at the indicated interim data time points; SAQ data will be sent at study completion, for all completing subjects. Medians, means and percentage values will be reported to decimal place (0.0) for all questionnaire data.

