Annex 11.3. Self-assessment Questionnaire

Answers given according to a 5-point scale: "5-completely agree 非常同意", "4-somewhat agree 比较同意""3-neither agree 说不上同意不同意", "2-somewhat disagree 比较不同意", "1-completely disagree 非常不同意"

Self-assessment - Pre-treatment	Yes/是	No/否	Comments/ 其他
术前 14 天产品使用问卷			, -
I feel skin is good prepared for procedure			
我觉得我的肌肤更强韧了,为特殊美容做好了准备			
I feel skin is comfort for procedure			
我觉得我的皮肤在特殊美容中更耐受了			
Skin feels intensively repaired			
肌肤感觉被深层修护			
I feel skin redness due to dryness is less occur?			
我感觉皮肤由于干燥而发红的情况减少了			
Skin feels strengthened			
肌肤感觉更强韧			
Skin feels hydrated			
肌肤感觉水润保湿			
Skin feels comfortable			
肌肤感觉舒服			
Skin feels smoother			
肌肤感觉更光滑			
Skin looks brighter			
肌肤看起来更明亮			
Skin looks more radiant			
肌肤看起来更有光泽			
Pores look less visible			
毛孔看起来不明显			
Skin feels more elastic			
肌肤感觉更有弹性			
Fine line looks less visible			
细纹看起来不明显			
Crow's feet wrinkle is reduced			
鱼尾纹看上去减少了			
Self-assessment - Recovery			
术前后 1 天,3 天,7 天,10 天恢复			
期问卷			
I feel pre-treatment with product help my skin recover fast			
after procedure			
我感觉提前14天使用产品,可以帮助肌肤在特殊美容后更			
快修复			
I feel pre-treatment with product help my skin recover			

		T
stable after procedure		
我感觉提前 14 天使用产品,可以帮助肌肤在特殊美容后更		
稳定		
I feel pre-treatment with product help my skin recover		
comfortable after procedure		
我感觉提前14天使用产品,可以帮助肌肤在特殊美容后更		
舒适		
I feel pre-treatment with product help my skin redness		
recovered		
我感觉提前14天使用产品,可以帮助肌肤在特殊美容后褪		
红		
I feel pre-treatmet with product help my skin dryness		
recovered		
我感觉提前14天使用产品,可以帮助肌肤在特殊美容后降		
低干燥爆皮		
I feel pre-treatment with product help my skin discomfort		
(e.g. red/dry/itch) from procedure recovered faster		
我感觉提前14天使用产品,可以使肌肤在特殊美容后的不		
适症状(如发红/干燥/瘙痒等)更快修复		
I would like to recommend my friends to use product before		
procedure		
我很乐意推荐我的朋友们,在特殊美容前使用产品		
I feel skin is comfort for procedure		
我觉得我的皮肤在特殊美容中更耐受了		
Self-assessment		
- Post-treatment		
术前7天及14天产品使用问卷		
Post-treat with product after skin recovered, skin feels		
smoother		
当肌肤在特殊美容恢复后,使用产品,肌肤感觉更光滑了		
Post-treat with product after skin recovered, skin feels		
brighter		
当肌肤在特殊美容恢复后,使用产品,肌肤感觉更明亮了		
Post-treat with product after skin recovered, skin feels		
more radiant		
当肌肤在特殊美容恢复后,使用产品,肌肤感觉更有光泽		
7		
Post-treat with product after skin recovered, skin pore is		
less visible		
当肌肤在特殊美容恢复后,使用产品,毛孔看起来不明显		
7		
Post-treat with product after skin recovered, skin feels		
more elastic		
当肌肤在特殊美容恢复后,使用产品,肌肤感觉更有弹性		

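### The annexed self-assessment form and its T15d timing conflict with the planned questionnaire analysis: Yes/No columns under a 1-5 scale, no product-neutral form for both groups, and a visit order that contradicts the schedule

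*Protocol*

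**What the plan says.** **Analysis (Protocol, section 8.3.1).** "Questionnaire response options will be in the form of a 5-point semi-structured scale", with 1 the least and 5 the most favourable rating and a neutral mid-point. Each item is tested with Shapiro-Wilk at 0.01. If normality is not rejected the mean is used; otherwise, "Responses that are not normally distributed will be assessed using the median response". The percentage of ratings 4 or 5 is also reported. On the analysis set: "For self-assessment questionnaires, only the data of completing subjects will be analyzed".

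**The form (Annex 11.3).** It opens with "Answers given according to a 5-point scale" and five labels from complete agreement (5) to complete disagreement (1). The table beneath has three answer columns: Yes, No and Comments. It has three blocks: pre-treatment, recovery (headed for days 1, 3, 7 and 10) and post-treatment. The first recovery item begins "I feel pre-treatment with product help my skin recover fast".

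**Who answers what, and when (section 5.6, repeated in the opening summary and section 4).** The efficacy and cosmeticity questionnaires are for Group 1 only. The third is for all groups (N=60): "Self-assessment questionnaire on post-procedure tolerance will be answered by subjects at T15d (Timm post-procedure"), then at T16d, T18d, T22d and T25d.

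**The T15d visit (section 7.2).** Step b reads "One questionnaire should be answered by subjects". The laser is step d. Clinical, imaging and instrumental assessments and the adverse-event check follow, with no further questionnaire. The schedule table in section 4 marks the self-assessment questionnaires under the post-procedure column of T15d.

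**The concern.** The form, the visit list and the analysis section describe different data collections. Three of the four problems arise when answers are collected, so they cannot be repaired at analysis. A Yes tick cannot later be turned into a 4 or a 5. An answer about a product the woman never used carries no information. A tolerance rating taken before the laser says nothing about tolerance of the laser. The fourth, the restriction to completers, is an analysis choice and can be changed until the analysis is run.

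At stake are the reported product ratings, including the top-box percentage, and the subjects' own account of recovery after the laser. Section 8.3.1 requires both to be summarised.

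**Working it through.** The protocol states no figure on this point to reproduce, so the check is mainly a comparison of sections.

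**1. Answer format.**
- Section 8.3.1 needs an integer from 1 to 5 for each item. The instruction at the head of Annex 11.3 supplies that scale; the columns below it supply two categories and a comment field.
- If the instruction is followed, all planned summaries can be computed. If the columns are followed, there is no rating of 4 or 5 to count.
- The normality step was checked for Yes/No answers at n = 30, the stated Group 1 size. For every split from 1:29 to 29:1, Shapiro-Wilk rejects at 0.01. The largest p-value is 2.2 × 10⁻⁷, at 15:15. Every item with mixed answers would therefore go to the median, which can only be Yes or No, or lie midway at exactly 15:15.

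**2. Recovery items set against respondents.**
- Of the 8 recovery items, 6 attribute recovery to pre-treatment with the product, 1 asks about recommending the product before a procedure, and 1 makes no reference to it. So 6 + 1 = 7 of 8 are product-worded.
- Under section 6.2, Group 2 receives no serum at any stage.
- At T16d, T18d and T22d the tolerance questionnaire is the only one section 5.6 schedules, and it is for both groups.
- The recovery block is the only part of Annex 11.3 carrying those days. It matches 4 of the 5 tolerance time points; T15d has no block at all.
- Annex 11.3 has no block titled as the tolerance questionnaire.

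Two readings remain. Either the recovery block is the tolerance questionnaire, and Group 2 is given items it cannot answer; or it is not, and the all-group form is missing from the annexes. On neither reading does the protocol contain a usable form for both groups.

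**3. Order at T15d.**

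| Source | Position of the T15d questionnaire |
|---|---|
| Summary, section 4, section 5.6 | Immediately post-procedure |
| Schedule table, section 4 | Post-procedure column |
| Visit list, section 7.2 | Step b, before the laser at step d; none after |

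If step b is the tolerance questionnaire, it precedes what it rates. If it is another form, the required post-laser questionnaire has no step in the visit list.

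**4. Completers only.**
- The protocol enrols 70 and requires at least 60 to finish, which leaves room for up to 70 − 60 = 10 leavers, or 10/70 = 14% of those enrolled.
- A woman who leaves after T25d may already have answered at up to six visits: T14d, T15d, T16d, T18d, T22d and T25d in Group 1. Under section 8.3.1 none of those answers would be analysed.

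**The case against.** The strongest reply is that a reader may infer more than the text supports. It deserves a point-by-point answer.

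- *The form is binary, so the analysis is impossible.* Not established. The five labelled options stand at the head of the same annex and match section 8.3.1. The form contradicts itself; the analysis fails only for answers ticked as the columns invite.
- *Untreated women are asked about the product.* No section assigns the recovery block to Group 2. The annexes evidently do not print every form: the cosmeticity questionnaire has no titled block, and section 5.2 locates a lactic acid questionnaire in Annex 11.4, which is in fact the tolerance diary. A missing tolerance form is therefore a fair reading, so no count of meaningless Group 2 answers can be given.
- *The T15d answer is taken before the laser.* Only the visit list points that way, and its questionnaire is unnamed.
- *The only patient-reported randomised comparison after the laser is lost.* This is wrong. Section 8.3.2 compares the groups on subject-scored lactic acid stinging, which is measured after the laser at T25d and T39d. It also compares them on tolerance feedback, whose fields match the diary columns of Annex 11.4. It does not list the self-assessment questionnaires.
- *Answers from leavers are deleted.* They are excluded from analysis; section 8.3.1 still lists raw data by subject.

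All of this stands and limits the point. The contradictions themselves remain, because none of these replies supplies a form with 1-5 answers, a neutral form for both groups, or a post-laser questionnaire step. The diary does not clearly fill the gap. The schedule footnote ties the arrows to the pre- and post-treatment fortnights, and the diary times symptoms from product use, although its last row runs from D15 to D56.

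**Conclusion.** The point holds as a set of contradictions to reconcile before forms are printed. Annex 11.3 conflicts with itself and with section 8.3.1 on the answer format. The protocol contains no product-neutral form for a questionnaire it requires from both groups at five time points: 7 of 8 items in the nearest block are product-worded, and T15d is not covered. The T15d visit list conflicts with the summary, sections 4 and 5.6 and the schedule table. The completer restriction discards valid earlier answers.

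The effect is limited to descriptive questionnaire results. The between-group comparisons in section 8.3.2 (clinical, instrumental, imaging, lactic acid and diary) are not touched. No numerical bias is claimed: the protocol gives no expected response or dropout pattern, and the 10 of 70 is its own allowance, not a forecast.

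Two assumptions matter. The column headings of Annex 11.3 are taken as they appear in the protocol text. Completing subjects are taken to be those who finish the study, which fits the later sentence in section 8.3.1 tying delivery of these data to study completion.

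**What to change.** 1. In Annex 11.3, replace the Yes and No columns with five boxes, 1 to 5, matching the labels above the table.
2. Annex a tolerance questionnaire for all groups with product-neutral items (for example, that the skin recovered quickly after the procedure), covering T15d as well as T16d, T18d, T22d and T25d. Keep product-worded items for Group 1 and state this on the form.
3. Reconcile the T15d list in section 7.2 with sections 4 and 5.6 and the schedule table, so that the tolerance questionnaire is answered after the procedure. If a pre-procedure questionnaire is also intended, name it.
4. In section 8.3.1, analyse every subject who answered at the visit concerned, with completers as a sensitivity analysis. This recovers earlier answers only; it cannot supply T39d answers for women who have left.

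The cost is one revised form, one reordered step and one changed analysis sentence, with no extra visits. Reported percentages may become slightly less favourable.

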8.3.2 Comparison between Treatments

Paired T test for the same sample size or the independent T test for the different sample size will be used to identify the difference efficacy between treatments if the data fit normal distribution.

- Group 1-Facial Serum group
- **Group 2-**Non-treatment control group

Evaluation	Attributes	Comparison
Clinical Assessment	•Skin symptoms scoring post-procedure: - Dryness - Erythema - Papules - Desquamation - Chromatosis - Edema - Escharosis •Skin qualities: - Skin elasticity - Skin evenness - Skin brightness - Skin smoothness - Skin radiance - Appearance of pores on cheek - Crow's feet wrinkle - Epithelial cell confluence - Over healthy appearance	Group 1 versus Group 2
Instrumental Assessment	Skin hydration by Corneometer Transepidermal water loss (TEWL) by Vapometer Skin elasticity by Cutometer Skin pH by Skin-pH-Meter	
Imaging Analysis	Attributes output from VISIA 7 Attributes output from OCT (The thickness of epidermis)	
LA stinging Test	•Skin symptoms scoring: - Stinging - Itching - Burning	
Tolerance Feedback	•Skin symptoms scoring: - Area - Severity - Start time - During time	

9. Further Study Documentation

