Investigator: Title: Dermatologist

[contact] [contact]

Test Site: China-Norm U@Test laboratory

Address: [name],

Shanghai, China

Study Objective: To evaluate the effect of a facial essence on skin barrier and skin condition after 2-week of use; And study on the repair efficacy of skin barrier and condition after receiving Fractional Ultrapulse CO₂-laser. The whole study will be divided into two dimensions to evaluate the product: the comparison of the effect before and after and the comparison with the control group.

Experimental Design:

Mono-centric, single-blind, parallel random and home use design.

Test Areas:

Whole face

Subjects:

70 female adult subjects will be enrolled and divided into 2 groups in the study, recruited according to inclusion and non-inclusion criteria listed below, and at least 60 subjects should complete the whole study (at least 30 subjects per group).

Group 1: Facial Serum Group

- Group 2: Non-treatment Group

Age: 20-50 years old

Measurements:

Clinical Assessment(N=60):

Skin qualities of skin dryness, erythema, papules, desquamation, chromatosis, edema, escharosis, elasticity, evenness, brightness, radiance, smoothness, pores on cheek, crow's feet wrinkle, epithelial confluence and overall healthy appearance will be evaluated by dermatologist at T0 (baseline), T14d (after pre-treatment), T15d (Timm post-procedure), T16d (1-day after self-recovery), T18d (3-day after self-recovery), T22d (7-day after self-recovery), T25d (10-day after self-recovery and product treatment start), T32d (7-day after product treatment), T39d (14-day after product treatment) for all groups.

Lactic Acid Stinging Test (N=60)

Sensitive level by Lactic acid test at T0 (baseline), T14d (after pre-treatment), T25d (10-day after self-recovery and product treatment start), T39d (14-day after product treatment) for all groups.

Instrument Assessment(N=60):

- **Corneometer:** skin hydration on both cheeks will be measured at T0 (baseline), T14d (after pre-treatment), T15d (Timm post-procedure), T16d (1-

day after self-recovery), T18d (3-day after self-recovery), T22d (7-day after self-recovery), T25d (10-day after self-recovery and product treatment start), T32d (7-day after product treatment), T39d (14-day after product treatment) for all groups.

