- 13. Must be willing to comply with all study protocol requirements (pay attention to: only use the skin care products provided during the study, not take topical or oral treatment like retinol, hormone, anti-oxidant health-care products which may affect the anti-aging efficacy of test serum).

Exclusion Criteria:

Prospective subjects meeting any of the criteria listed below will be excluded from participation:

- 1. Pregnant or breast-feeding woman or woman planning pregnancy during the study.
- 2. Subject deprived of rights by a court or administrative order.
- 3. Major subject to a guardianship order.
- 4. Subject residing in a health or social care establishment.
- 5. Patient in an emergency setting.
- 6. Subject with a skin disease in the test areas as well as skin allergy (particularly e.g., acne, rosacea, eczema).
- 7. Volunteer presenting a stable or progressive serious disease (per investigator's assessment).
- 8. Immuno-compromised subject.
- 9. Subject has hyperpigmentation skin symptoms.
- 10. Subject with history of allergy to cosmetic or personal care products or ingredients.
- 11. Subject presenting excessive exposure to sunlight or UV radiation (investigator's assessment).
- 12. Subjects regularly practicing aquatic or nautical sports.
- 13. Subjects regularly attending a sauna.
- 14. Subject with physical highly sensitive constitution;

¹Declaration of Helsinki, 64th World Medical Assembly, Fortaleza, Brazil, October 2013

- 15. Subject with cardiovascular or circulatory history.
- 16. Subject with a history of skin cancer or malignant melanoma.
- 17. Subject with history of medical beauty treatment and taking part in anti-aging studies in the last 3 months before study.
- 18. Intake of antihistamines, antibiotics, corticosteroids, non-steroidal anti-inflammatories or immune-suppressants in the last 6 months before study.

4. Study Design

70 female adult subjects will be enrolled and divided into 2 groups in the study, recruited according to inclusion and non-inclusion criteria listed below, and at least 60 subjects should complete the whole study (at least 30 subjects per group).

• Clinical Assessment(N=60):

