7.2. Conducting the Study

Pre-screening visit at T-7d

- a. Within 24 hours before screening visit, subjects will be asked not to use any cosmetic product on test areas.
- b. On the arrival, the subject will be informed about the nature of the study and the treatment procedure and a signed and dated informed consent form will be obtained. At the same time, one Photo release form will be also signed from each subject.
- c. A subject screening number will be automatically allocated (SC0X) by CRF.
- d. Demographic data collection.
- e. Medical examination, subject's interview on his medical history and concomitant medications.
- f. Subjects wash face with usual cleanser, then pat dry with clean tissue paper at center.
- g. Acclimatization to the room condition for 30 minutes (the conditions with a well-controlled room temperature (21 ± 1 °C) and humidity ($45\%\pm5\%$).
- h. Clinical assessment by will be done by dermatologist for screening.
- i. Verification of subject eligibility: inclusion/non-inclusion criteria and on-site clinical grading by Dermatologist.
- j. The weighted wash-out products and daily log will be delivered to each subject.
- k. Adverse Events/Local Intolerance will be checked and recorded.

Evaluation visit on T0: Baseline

- a. Subjects wash face with usual cleanser, then pat dry with clean tissue paper at center.
- b. Acclimatization to the room condition for 30 minutes (the conditions with a well-controlled room temperature (21 ± 1 °C) and humidity ($45\%\pm5\%$).
- c. Verification of inclusion/non-inclusion criteria for final eligibility.
- d. Clinical Assessment will be done by dermatologist for T0.
- e. VISIA 7 will be done by trained technician for T0.
- f. OCT scan will be done by trained technician for T0.
- g. Corneometer will be done by trained technician for T0.
- h. Vapometer will be done by trained technician for T0.
- i. Cutometer will be done by trained technician for T0.
- j. pH meter will be done by trained technician for T0.

- k. LA sting test will be done by trained technician for T0.
- The wash-out (standard) products will be weighted and returned to subjects; as the same time, the weighted
 investigational products and daily log will be delivered to each subject according to the randomization
 table.
- m. Adverse Events/Local Intolerance will be checked and recorded.

T0 to T14d

a. Subjects should apply the provided wash-out products twice a day at home, in the morning and in the evening.

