8.1. Statistical considerations

All statistical tests will be two-sided and at the 5% level of significance.

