A more appropriate analysis may be performed, which will be recorded in a Note to File and/or in the study report.

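### The between-group t-test is chosen by whether the two groups have equal numbers, so normally distributed endpoints could get a paired test on unrelated women, with a p-value that depends on row order

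*Protocol*

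**What the plan says.** Section 8.3.2 gives the rule for comparing Group 1 (facial serum) with Group 2 (non-treatment): "Paired T test for the same sample size or the independent T test for the different sample size will be used". The rest of that sentence limits the rule to normally distributed data. So there are two conditions. The data must be normal, and equality of the two sample sizes then decides between the paired and the independent test. The table that follows applies the comparison to clinical scores, instrumental readings, imaging outputs, lactic acid stinging and tolerance feedback.

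The design is described elsewhere in the protocol:
- The synopsis, under Experimental Design: "Mono-centric, single-blind, parallel random and home use design".
- Section 4, on enrolment: "70 female adult subjects will be enrolled and divided into 2 groups in the study". Its target for completion is that "at least 60 subjects should complete the whole study (at least 30 subjects per group").
- Section 7.2, baseline visit, where a pre-set list governs supply: "investigational products and daily log will be delivered to each subject according to the randomization".

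Section 8.1 sets the error level: "All statistical tests will be two-sided and at the 5% level of significance". Section 8.3.1 closes with a general reservation: "A more appropriate analysis may be performed, which will be recorded in a Note to File and/or in the study report".

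**The concern.** Pairing is a property of the design. A paired t-test needs a reason why one observation belongs with another, such as the same woman, two sides of one face, or a matched partner. The protocol gives no such link between a woman in Group 1 and a woman in Group 2. Equal counts do not supply one.

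Under the rule, dropout and missing values choose the test, and the order of rows in the data set chooses the pairs. The protocol fixes no row order. Two analysts who both follow 8.3.2 faithfully could therefore report different p-values, and in borderline cases opposite verdicts, from the same data. If numbers are counted by endpoint and visit, the test could also switch between lines of one results table. Comparison with the control group is one of the two dimensions named in the study objective, so this matters for the main reading of the trial.

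**Working it through.** **Inputs.** From the protocol: two-sided alpha 0.05; 70 women enrolled; at least 30 completers per group. The protocol gives no effect size, standard deviation or power, so it has no figure to reproduce. Everything below that needs such a value uses an assumption, and all data are simulated normal data, not trial data.

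**1. How often the paired branch is reached.** Assume 35 women per arm (the protocol does not state the split) and independent dropout with the same probability in each arm. Then P(equal completers) = Σ P(K = k)², with K binomial(35, dropout).

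| Assumed dropout | P(equal numbers) |
|---|---|
| 5% | 23% |
| 10% | 16% |
| 14.3% (= 10/70, the loss implied by 70 enrolled and 60 completing) | 14% |

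It would be higher if the site aims for exactly 30 per group.

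**2. What pairing does to one data set.** With equal standard deviations, t(paired) = t(independent) / √(1 − r), where r is the sample correlation that the chosen row order happens to produce. Degrees of freedom fall from 58 to 29, and the critical value rises from 2.002 to 2.045.

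Take 30 v 30 with independent-test p = 0.048, so t = 2.020. For 30 arbitrary normal pairs, r lies between −0.463 and +0.463 in 99% of orders.
- r = +0.463: t = 2.020/√0.537 = 2.756, p = 0.010 (29 df).
- r = −0.463: t = 2.020/√1.463 = 1.670, p = 0.106.
- p < 0.05 needs r above 1 − (2.020/2.045)² ≈ 0.024, which holds in about 45% of orders.

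Shuffling simulated data 20,000 times gives the same picture: central 99% of paired p from about 0.01 to 0.11, with about 45% of orders below 0.05.

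This example sits at the threshold on purpose. In other simulated sets, 83% of orders were below 0.05 when the independent p was 0.03, 41% when it was 0.050, and 10% when it was 0.08.

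**3. Long-run behaviour with an arbitrary order fixed beforehand.** In 40,000 simulated trials under the null, type I error was 4.9% for the paired test and 4.8% for the independent test. At an assumed standardised difference d = 0.736, the noncentrality is 0.736/√(2/30) = 2.851. Power is 80.0% with 58 df and 78.7% with 29 df. The two tests gave different verdicts in 1.6% of trials under the null and in about 4% to 6% at d = 0.5 to 0.8.

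**4. When row order is related to outcome.** Suppose both lists are sorted in the same direction by a variable with correlation r to the outcome (assumed values). Type I error of the paired test is then:

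| r | Type I error |
|---|---|
| 0.2 | about 5% |
| 0.4 | about 7% |
| 0.6 | about 11% |
| 0.8 | about 21% |

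At r = 0.6, sorting only one list leaves it at about 5%, and sorting the lists in opposite directions lowers it to about 2%.

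**The case against.** Several limits are real, and they stand.

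- **Reach.** A reader might infer that every Group 1 versus Group 2 result would come from an invalid test. The text does not support that. The rule covers only normally distributed data, and many listed endpoints are coarse scores (symptoms 0 to 5 in section 5.1, stinging 0 to 3 in section 5.2) that may well fail a normality test. Equal numbers are needed too, and under the assumptions above they are the less likely outcome.
- **False positives.** A reader might also infer that the rule inflates the false-positive rate. It does not in the ordinary case: with a pre-fixed order unrelated to outcome, a paired test on independent groups keeps its level. Inflation needs both lists sorted in the same direction by something related to outcome, and nothing in the protocol calls for such sorting. Section 8.3.1 says only that raw data are listed by subject.
- **Frequency of conflict.** The wide range of p-values belongs to a result near 0.05. Across trials the two tests usually agree.

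Two other defences do not hold. The reservation about a more appropriate analysis closes 8.3.1, names no method and leaves the decision to a file note or the report, so it does not correct 8.3.2. Nor can 'paired' be read as within-subject: those comparisons have their own section, 8.3.1, while 8.3.2 names the two groups.

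**Conclusion.** The rule in 8.3.2 is wrong as written and should be corrected. This is not a detail left to an analysis plan, because the protocol fixes the choice of test and fixes it on the wrong criterion. The damage is bounded. It arises for normally distributed endpoints when group numbers are equal, about 14% to 23% of trials under the assumed 35 per arm and 5% to 14.3% dropout. There the p-value is not determined by the data alone, which leaves room for choice after the results are seen. The routine cost is small: about one point of power at the assumed d = 0.736, and type I error near 5%. The larger error rates in step 4 depend on same-direction sorting and on assumed correlations, and are a possibility rather than an expected result.

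**What to change.** Delete the sample-size rule from section 8.3.2 and state:

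*All Group 1 versus Group 2 comparisons use independent-groups methods whatever the group sizes; paired methods are used only for the within-subject comparisons in 8.3.1.*

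Each data set then has one p-value that does not change with row order, and at 30 per group the pooled t-test keeps its 58 degrees of freedom. The cost is one sentence of wording, with no new data, visits or subjects. It should be made before the group results are seen.
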